4.2.1 Subchronic Toxicity

In two studies conducted in CD rats and beagle dogs, rats received daily gavage doses of 0, 200, 400, or 1000 mg/kg bw of resveratrol for 90 days while dogs received daily orally doses of 0, 200, 600, or 1200 mg/kg bw of resveratrol for 91 days. No mortality was seen in either study nor were there any clinical observations of treatment-related gross toxicities. Female rats in all dose groups experienced a reduction in body weight during weeks 10-13; however, females at the highest dose experienced statistically significant decrease in body weight. For both male and female dogs, there was a statistically significant decrease in body weight at the highest dose that started at week 5 in male dogs and at week 6 in female dogs. Other clinical findings for rats included a small, but statistically significant increase in mean total bilirubin levels in both sexes of rats in the high dose group at study termination. Additionally, a modest but statistically significant and dose-related hepatomegaly was seen in both male and female rats. There was no evidence of any neurotoxicity in either sex. For dogs, only minimal toxicity was seen. Treatment-related changes were limited to inflammatory infiltrates in the urinary bladder and kidneys of which the severity ranged from minimal to mild with most dogs demonstrating only changes of minimal severity. No other changes were noted in other organs or tissues. The NOAEL for rats was determined to be 200 mg/kg/day and 600 mg/kg/day for dogs. The NOAEL for both species was determined on the decreases in body weight.¹³

4.2.2 Chronic Toxicity

A 6-month rat study was conducted using oral doses of resveratrol at 300, 1000, and 2,000 mg/kg/day or placebo. Weight loss occurred in the 2,000 mg/kg group. Total bilirubin values were increased in the 1000 mg/kg group with the values returning to normal after the recovery period. The NOAEL was considered to be 300 mg/kg/day.¹² Another 6-month study using oral daily doses of 100, 300, and 500 mg/kg or placebo was conducted in rabbits. No drug-related mortality was observed during the study and there were no apparent drug-related clinical abnormalities. For animals in the 500 mg/kg dose group, modest increases were seen in clinical chemistry parameters of total protein, albumin, GGT, globulin, glucose, urea nitrogen, indirect bilirubin and calcium along with decreases in potassium, but these findings were not present in the recovery animals. The NOAEL was considered to be 500 mg/kg/day.¹²

4.2.3 Reproductive Toxicity

A study was conducted in rats using oral daily doses of 300, 1000, and 3000 mg/kg or placebo administered on days 7 through 17 of presumed gestation. Five of the 25 animals in the 3000 mg/kg dose group were sacrificed due to adverse clinical conditions. No effects on the fetus were noted. The maternal NOAEL was considered to be 300 mg/kg/day and the developmental NOAEL was considered to be 1000 mg/kg/day.¹²

4.3 Clinical

4.3.1 Safety

In a 12-week clinical study in Friedreich's ataxia patients including 27 participants who received the study drug, 24 completed the study. Thirteen patients received 1 g/day of resveratrol while the other 14 patients received 5 g/day of resveratrol. No serious adverse events were noted.

Gastrointestinal (GI) side effects were the most frequent occurring adverse effects and were deemed to be dose-related.

The following side effects were seen in 2% to 15% (except if otherwise stated) of the 13 patients with Friedreich's ataxia taking resveratrol 500 mg twice daily (total daily dose: 1000 mg) for 12 weeks:

Infections

- Urinary tract infection (23%)
- Tonsillitis (inflammation of tonsil)
- Inflammation of the sinus (sinusitis)

Nervous system disorders

- Headache (31%)
- Fatigue (23%)

Gastrointestinal disorders

- Loose stools
- Abdominal pain/cramps
- Bloating
- Diarrhea
- Nausea
- Indigestion/upset stomach

Respiratory disorders

- Upper respiratory tract infection (31%)

Cardiac disorders

- Rapid and irregular heartbeat
- Increase in the level of substances (called enzymes) in blood that may indicate heart problems

Kidney and urinary disorders

- Proteins in urine

Liver, gallbladder or pancreas disorders

- Increase in the level of substances (called enzymes) in blood that may indicate liver problems

Overall, 1,000 mg/day resveratrol was well tolerated.¹⁴

Another randomized, placebo-controlled, double-blind, multicenter 52-week trial of resveratrol in subjects with mild to moderate Alzheimer's disease examined the drug's safety and tolerability. A total of 119 individuals were randomized and 104 completed through to week 52. Fifty-five subjects received placebo. The starting dose was 500 mg/day of resveratrol or matching placebo. The dose was escalated at 500 mg increments every 13 weeks as follows: 500 mg/day am; 500 mg twice a day; 1000 mg am and 500 mg pm; and 1000 mg twice a day. No differences between the resveratrol and placebo groups were found on vital signs, physical examinations, or neurologic examinations.

The side effects that were seen in 2% to 15% (except if otherwise stated) of the 64 patients with mild to moderate Alzheimer's disease who received resveratrol and in equal or greater frequency than in the placebo group are listed below. These patients were taking resveratrol 500 mg/day ending with 1000 mg twice daily (total daily dose of resveratrol: 2000 mg).¹⁵

Infections and infestations (42%)

Nervous system disorders (39%)

- Headache

Gastrointestinal disorders (42%)

- Diarrhea (41%)
- Nausea

Psychiatric disorders (36%)

General disorders

- Weight loss (17%)
- Fall (34%)

Respiratory problem (20%)

Vascular disorders

4.3.2 Pharmacokinetics

There are many published human studies dealing with the pharmacokinetics, metabolism, and disposition of resveratrol. Absorption, bioavailability, and metabolism of ¹⁴C-resveratrol after oral and intravenous (IV) doses was investigated in six human volunteers. The absorption of a dietary relevant 25-mg oral dose was at least 70%, but poorly bioavailable ($\leq 1\%$).^{6,16} Peak plasma concentrations of trans-resveratrol were reached at 0.8-1.5 h following oral trans-resveratrol administration at doses 25, 50, 100 or 150 mg, six times/day.¹⁷ A second peak of plasma concentration occurring at 6 hours after the oral dose (but not after the IV dose) may be due to enterohepatic recirculation of conjugated metabolites by reabsorption after intestinal hydrolysis.¹⁶ Absorption is reduced when resveratrol is given with a high fat meal with a delayed time of peak plasma concentrations.¹⁸ There was an increase in systemic exposure to trans-resveratrol with increasing doses of 25-150 mg. Over this dose range, there was a more than dose-proportional increase in AUC_{0-t} and C_{max}. The dose proportionality factor was 2.8 for C_{max} and 6.6 for AUC_{0-t} following a single dose. With repeated doses, steady-state was reached at least by dose 7.¹⁷

Resveratrol has poor water solubility and thus has to be bound to plasma proteins to assure its body distribution and bioavailability. The plasma protein binding of resveratrol in human plasma was 98%.¹⁹

Following oral trans-resveratrol, three metabolic pathways were identified, i.e., sulfate and glucuronic acid conjugation of the phenolic groups and hydrogenation of the aliphatic double bond, the latter likely produced by the intestinal microflora. There was no evidence of enzymatic

oxidation of resveratrol. The rapid appearance of a sulfate conjugate pair in plasma at 2 hours after either IV or oral doses suggests that sulfation by the intestine/liver may indicate a rate-limiting step in resveratrol's bioavailability. Although presystemic metabolism of resveratrol may be important for the oral dose, iv doses also demonstrate highly efficient systemic metabolism. In humans, the major metabolites were the glucuronide- and sulfate-conjugates of resveratrol and of dihydro-resveratrol, with most of the dose (64 to 70%) recovered in the urine. The total recovery of glucuronic and sulfate conjugations in human urine and feces was about 83 % after oral doses and 74 % after intravenous doses. Resveratrol was shown to inhibit the phenotypical index of CYP3A4, CYP2D6 and CYP2C9 and was able to induce the phenotypical index of CYP1A2. On the other hand, GST and UGT1A1 activity was minimally affected.²⁰ Most of the oral dose was recovered in urine. Plasma half-life is 9.2 ± 0.6 hours.¹⁶ An almost complete elimination of resveratrol and its metabolites from tissues is observed by 72 h after a single dose.²¹

Additional PK parameters are shown in [Table 1](#) and concentration versus time profiles in [Figure 1](#).²² Further detailed PK information can be found in the Investigator Brochure.¹⁰

4.4 Rationale for Study Conduct

Absorption of micronized resveratrol is good (~70%) but the compound is almost totally eliminated by first pass metabolism, primarily to glucuronides and sulfates.¹⁰ One of the biggest challenges in translating the therapeutic effects of resveratrol is the poor bioavailability of the drug when it is administered orally. Resveratrol is eliminated from the body extremely quickly and maintaining a therapeutic level in the bloodstream is difficult.^{16,23} In an attempt to improve the oral bioavailability of resveratrol, various formulations and drug delivery systems have been tested but none have been forthcoming, with the exception of multiparticulate formulations, which have shown increased bioavailability.²⁴ Results have shown that high doses of resveratrol are needed to affect disease state; however this causes serious side effects that limit treatment utilization. To bypass the first pass effect, a micellar formulation could allow access to lymphatic distribution. The structure of the product micelle, with a size of appr. 30 nm, is similar to the structure of the naturally formed physiological mixed micelles containing water-insoluble compounds in its core which is enclosed by ambiphilic molecules. The higher bioavailability, which is obtained by the product micellation, is based on the independence of this transport system from the limiting parameters in the formation of the physiological mixed micelle. It is important to appreciate the product micelle's character as an "encapsulation and transport medium". This must not be confused with "nanoparticles" which are often spoken about in nanotechnology. Jupiter Orphan Therapeutics (JOT) is developing a new formulation (called JOTROL) of trans-resveratrol (3,4',5-trihydroxy-trans stilbene) for the treatment of Mucopolysaccharidosis type I (MPS I) and Friedreich ataxia (FRDA). JOTROL is a micellar 10% resveratrol solubilization formulation that is thought to increase the amount of resveratrol and metabolite concentrations in the blood via the lymphatic system.¹⁰

4.5 Rationale for the Study Population

As above mentioned, published data have shown that resveratrol protects against some neurodegenerative diseases, such as Alzheimer's disease and obesity as well as is effective in the management of osteoporosis in post-menopausal women. In order to assess the potential clinical

use of resveratrol in usual populations with these medical conditions, the upper age limit of study participants will be 75 years.

Since there have been no studies with pregnant women, it is uncertain whether there is human fetal risk associated with the use of resveratrol. Therefore, non-pregnant, non-lactating females will be included in the study. In addition, females of childbearing potential will be included if they use appropriate methods of contraception.

Given the fact that smoking may alter the metabolism of resveratrol, smokers will not be included in this study.

Table 1 Plasma PK of Resveratrol, Two Resveratrol Monoglucuronides and Resveratrol 3-sulfate After Single Oral Doses of Drug

[figure not shown]
Variable	Dose level (g)			
	0.5	1.0	2.5	5.0
Resveratrol				
AUC _{inf} (ng h/mL)	223.7*	544.8 (57.2)	786.5 (36.2)	1,319 (59.1)
C _{max} (ng/mL)	72.6 (48.9)	117.0 (73.1)	268.0 (55.3)	538.8 (72.5)
T _{max} (h)	0.833 (0.5-1.5)	0.759 (0.5-4.0)	1.375 (0.5-4.0)	1,500 (0.67-5.0)
C _{av} (ng/mL)	8.36 (57.8)	18.04 (51.6)	32.25 (43.0)	51.90 (80.7)
Half-life (h)	2.85*	8.87 (91.1)	4.22 (51.6)	8.52 (95.8)
CL/F (L/h)	2,235*	2,593 (65.1)	3,471 (29.9)	4,930 (50.0)
CL _R (L/h)	1.177 (102.5)	0.696 (71.5)	0.656 (53.1)	1.443 (139.2)
V/F (liters)	9,198*	19,298 (54.3)	22,226 (67.3)	66,991 (112)
Glucuronide 1				
AUC _{inf} (ng h/mL)	1,919 (33.6)	3,059 (60.9)	5,664 (27.7)	9,923 (40.9)
C _{max} (ng/mL)	404.6 (35.3)	473.6 (76.8)	874.4 (37.5)	1,285 (55.4)
T _{max} (h)	2.00 (1.0-6.0)	2.250 (1.0-6.0)	2.375 (1.0-8.0)	2.00 (1.5-5.0)
C _{av} (ng/mL)	76.9 (37.2)	110.3 (56.1)	215.5 (43.5)	344.1 (51.5)
Half-life (h)	2.85 (48.6)	7.27 (93.9)	10.6 (92.9)	7.90 (39.1)
CL/F (L/h)	282.7 (27.3)	493.5 (74.7)	469.5 (25.7)	590.6 (45.2)
Glucuronide 2				
AUC _{inf} (ng h/mL)	1,287 (21.7)	2,589 (66.4)	4,320 (32.9)	8,546 (62.3)
C _{max} (ng/mL)	369.5 (39.6)	672.6 (81.1)	1,626 (71.5)	1,735 (66.4)
T _{max} (h)	1.500 (1.0-5.0)	1.750 (1.0-5.1)	2.000 (1.0-6.0)	2,520 (1.5-8.0)
C _{av} (ng/mL)	51.0 (27.6)	99.9 (66.2)	193.8 (39.3)	317.8 (65.6)
Half-life (h)	3.09 (69.8)	6.64 (92.1)	8.42 (88.9)	5.83 (51.2)
CL/F (L/h)	408.8 (26.7)	642.5 (83.0)	636.9 (32.6)	1,017 (94.6)
3-Sulfate				
AUC _{inf} (ng h/mL)	4,049 (26.6)	10,053 (73.2)	16,984 (41.7)	30,898 (46.1)
C _{max} (ng/mL)	1,135 (25.7)	2,102 (81.3)	2,786 (27.2)	4,294 (48.0)
T _{max} (h)	1.500 (1.0-5.0)	2.000 (1.0-5.0)	2.000 (1.0-5.2)	2,050 (1.0-6.0)
C _{av} (ng/mL)	172.0 (23.2)	402.6 (70.5)	597.0 (27.0)	1,089 (49.4)
Half-life (h)	3.21 (56.6)	4.51 (82.8)	11.5 (95.5)	7.71 (42.3)
CL/F (L/h)	131.2 (25.8)	151.8 (62.7)	171.2 (40.0)	207.8 (63.9)

NOTE: Values are the mean of *n* = 10 with coefficient of variation (in percent) or range in brackets.

Abbreviations: AUC_{inf}, area under the concentration versus time curve to time infinity; C_{max}, maximal plasma concentration; T_{max}, median time of maximal plasma concentration; C_{av}, average plasma concentration; CL/F, apparent total body clearance (calculated as dose/AUC_{inf}); CL_R, apparent renal clearance approximated by amount excreted with urine within 24 h over AUC₀₋₂₄; V/F, apparent volume of distribution.

**n* = 1, value for AUC_{inf} at the lowest dose could be established in only one participant.

Figure 1 Mean Plasma Concentrations of Resveratrol (A), Two Resveratrol Monoglucuronides (B and C), and Resveratrol-3-sulfate (D) Versus Time in Healthy Volunteers Who Received a Single Dose of Resveratrol at 0.5, 1.0, 2.5, or 5.0 g Doses.

5. Objectives

The objectives of this study are:

- To characterize the PK profile of JOTROL (resveratrol) following oral administration of SAD ranging from 200 mg up to a dose currently estimated at 1000 mg, in healthy adult subjects;
- To evaluate the effect of food on the PK profile of JOTROL.

6. Study Design

This will be a single center, Phase 1, open-label, sequential SAD study, with a food-effect arm. The study will be divided into two parts:

- Study Part 1 consists of 3 periods with SAD of JOTROL under fasting conditions. Periods 2 and 3 will be initiated with updated doses after safety, tolerability, and PK data are evaluated by the Safety Committee **and the DSMB** and deemed acceptable for single doses for subsequent doses.
- Study Part 2 consists of a single oral JOTROL dose under fed conditions. JOTROL dose for this study part will derive from study Part 1 safety, tolerability, and PK data.

This study is intended for filing under FDA regulations.

7. Rationale for Dose Selection

7.1 Starting Dose

Diarrhea or other gastrointestinal symptoms were reported in clinical studies in healthy volunteers at doses of 1,000 mg/day or higher of unmodified resveratrol. Studies do not indicate significant adverse effects below 1,000 mg.^{20,25} In addition, results of metabolic interactions with cytochrome P-450 complex enzymes at doses higher than 1,000 mg/day suggested that this dose of unmodified resveratrol is the upper limit for clinical studies.²⁰ Considering different NOAEL values obtained with different animal species in subchronic and chronic toxicity studies (sections 4.2.1, 4.2.2, and 4.2.3) that are within 200 mg/kg and 700 mg/kg²⁵ it may be assumed that resveratrol shows a good safety profile within a certain range dose. In addition, a dose of 50 mg/kg of study product JOTROL administered to rats produced an AUC (2.5 µg•hr/mL) roughly equivalent to that seen after a 2,500 mg dose in humans.¹⁰ Applying a security factor of 10, the entry dose might be 250 mg. Consequently, a starting dose of resveratrol 200 mg can be considered safe.

7.2 Maximum Dose in this Study

The FDA preliminary review of the published data on resveratrol shows that the nonclinical data can only support daily oral doses of unmodified resveratrol (i.e. non-micronized drug with no absorption enhancers) of up to 3,000 mg/day for no more than 13 weeks. Published data from a 26-week study in mice demonstrated renal toxicity at 1,000 mg/kg/day, for which the Human Equivalent Dose is approximately 5,000 mg. Based on published data in healthy volunteers, AUC exposures at a dose of 3,000 mg/day of unmodified resveratrol is estimated to be

2.1 $\mu\text{g}\cdot\text{hr}/\text{mL}$. Because JOTROL formulation has been modified to enhance bioavailability, JOTROL doses to be used in this study should produce AUC exposures less than 2.1 $\mu\text{g}\cdot\text{hr}/\text{mL}$.²⁶

7.3 Dose Escalation Scheme (Study Part I)

The dose escalation scheme for this SAD study (Part 1) was established considering the following assumptions:

- PK animal data (rat, with a dose of 50 mg/kg) suggest that resveratrol administered as JOTROL produce an AUC (2.5 $\mu\text{g}\cdot\text{hr}/\text{mL}$) roughly equivalent to that seen after a 2,500 mg dose in humans;
- AUC exposures at a dose of 3,000 mg/day of unmodified resveratrol is estimated to be 2.1 $\mu\text{g}\cdot\text{hr}/\text{mL}$. AUC exposures during this study must not be higher than 2.1 $\mu\text{g}\cdot\text{hr}/\text{mL}$;
- The bioavailability of resveratrol from JOTROL increases linearly with the dose.

The nominal planned dose escalation scheme for Study Part I corresponds to a 2.5-fold increment between the two first doses, and 2 fold increment between the second and third dose levels. Both current second and third dose levels are nominal as JOTROL's doses to be administered in Periods 2 and 3 will be reassessed when safety, tolerability, and PK data analysis are available. These dose levels will be adjusted, lowered or increased, but in any case corresponding AUC exposures must be lower than 2.1 $\mu\text{g}\cdot\text{hr}/\text{mL}$.

7.4 Dose Level in Study Part II

The same dose is planned to be administered in Periods 3 (Part I) and 4 (Part 2). However, if the exposure is higher than expected in Period 3, the dose to be administered in Period 4 could be lower, in order to keep AUC exposures lower than 2.1 $\mu\text{g}\cdot\text{hr}/\text{mL}$, as specified in section 7.2.

7.5 Dose Escalation Criteria

Each dose level will be dosed sequentially in an ascending fashion, with at least 14 days between dosing of consecutive dose levels. Following completion of each level, safety, tolerability, and PK data will be evaluated by a Safety Committee **and a DSMB** before proceeding to the next dose. The Safety Committee **and the DSMB** will review the whole safety and tolerability data, as well as PK data up to 32 hours post-dose, in order to make decisions regarding progression to the next prescribed dose level, decreasing the next dose level, repeating a dose level or not evaluating any additional dose level, based on consideration of the clinical significance of several safety and tolerability parameters, as well as PK data. The Safety Committee will be composed by at least the Investigator, one medically qualified Sponsor representative, and an independent third party physician. **A formal DSMB will also be established and constituted by an independent group of experts (totally independent of Syneos Health, JOT, and the associated investigators on the study) that advises the NIA Director and the study investigator. The members of the DSMB serve in an individual capacity and provide their expertise and recommendations. The DSMB will be constituted and will act according to the FDA Guidance for Clinical Trial Sponsors - Establishment and Operation of Clinical Trial Data Monitoring Committees¹ and the NIA Guidance on Clinical Trials.²** Dose

escalation may occur only following mutual agreement between the Safety Committee **and the DSMB** members.

Minutes of the safety review committee meeting **and the DSMB** will be prepared and signed by all voting participants. Minutes will include the decision to escalate the dose, confirmation of the next dose level, confirmation of the safety monitoring and washout period, rationale for the decisions and supportive data. The minutes will be shared with the Independent ethics committee (IEC)/Institutional review board (IRB).

Some adjustments to the currently outlined doses may be implemented by the Safety Committee, **or the DSMB** but the dose to be administered at a given dose level will not exceed the dose corresponding to AUC exposures of 2.1 $\mu\text{g}\cdot\text{hr}/\text{mL}$.

Stopping Rules for Dose Escalation

Dose escalation will be halted if any of the events described below occur within one dose level:

- Individual stopping rules met for ≥ 2 subjects in the same study period suggesting that subjects receiving higher dose levels would be at risk for similar adverse drug reactions.
- The occurrence of one serious adverse event (SAE) considered at least possibly related to the study drug.
- The occurrence of severe AEs considered at least possibly related to the study drug in ≥ 2 subjects and independent of within or not within the same system organ class (SOC).
- Clinically significant abnormalities of the same character, at least of moderate severity, and considered at least possibly related to the study drug in ≥ 2 subjects

Cumulative Study Events

In addition to the events listed above, any of the events described below occurring at different dose levels administered throughout the study (i.e., cumulative events) will also result in a temporary halt of dose escalation:

- The occurrence of severe AEs of the same character considered at least possibly related to the study drug in ≥ 2 subjects.
- Clinically significant abnormalities of the same character, at least of moderate severity, and considered at least possibly related to the study drug in ≥ 3 subjects
- Determination by the SRC that a pattern of AEs precludes further dose escalation, even if no other stopping rules have been met.

Study Stopping Rules

The study will be terminated if any of the following criteria are met:

- The occurrence SAEs considered at least possibly related to the study drug in ≥ 2 subjects and independent of within or not within the same SOC.

- Determination by the SRC that a pattern of AEs precludes any further dosing.

8. Study Population

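### Seven of the nine stopping criteria in Protocol 7.5 act on dose escalation only, so meeting one at the Period 3 dose places no automatic hold on Period 4, which is planned to repeat that dose, fed, in 16 subjects

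*Protocol*

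**What the plan says.** Protocol 7.5 has three groups of criteria.

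- **Within one dose level** (four criteria): "Dose escalation will be halted if any of the events described below occur within one dose level". One of the four is "The occurrence of one serious adverse event (SAE) considered at least possibly related to the study drug". Another is severe related AEs in two or more subjects. The first, on individual stopping rules, is framed as "suggesting that subjects receiving higher dose levels would be at risk for similar adverse drug reactions".
- **Cumulative across levels** (three criteria): meeting one "will also result in a temporary halt of dose escalation".
- **Study stopping rules** (two criteria): the study ends. One is "The occurrence SAEs considered at least possibly related to the study drug in ≥ 2 subjects"; the other is a committee judgement that the AE pattern rules out any more dosing.

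The agreement rule in the same section is also limited to increases: "escalation may occur only following mutual agreement between the Safety Committee" and the DSMB.

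On the doses, Protocol 7.3 states: "The nominal planned dose escalation scheme for Study Part I corresponds to a 2.5-fold increment between the two first doses", followed by a 2-fold step to the third level. It describes no step beyond that. On Period 4, Protocol 7.4 states: "The same dose is planned to be administered in Periods 3 (Part I) and 4 (Part 2"). The only ground it gives for a lower Period 4 dose is exposure above expectation, measured against the 2.1 µg·hr/mL AUC limit. Protocol 9.5 assigns the 16 Part 2 subjects the top Part 1 dose and permits, without requiring, a reduction on safety, tolerability or PK grounds.

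**The concern.** The rules with a fixed consequence are all tied to going up in dose, except for the two that end the study. After Period 3 there is no planned increase left, but one planned administration remains, at the same dose and under a new condition. The criteria therefore stop binding at the level where they are most likely to be needed. Protocol 7.1 notes gastrointestinal symptoms with unmodified resveratrol at 1,000 mg/day and above, and 7.2 notes that JOTROL is modified to raise bioavailability. The AUC limit constrains exposure; it does not respond to tolerability events that occur below it.

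At stake is the redosing of 16 healthy subjects after an event pattern that the sponsor judged serious enough to compel a halt at the two earlier steps. The protocol gives no reason for treating the last step differently. The same gap applies if a Part 1 level is repeated, which 7.5 lists as an option: a repeat is not an increase either.

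**Working it through.** The protocol states no operating characteristics for these rules, so there is no figure to reproduce. The check is a count, then a comparison of the same event at two dose levels.

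**Step 1. Count the criteria by consequence (Protocol 7.5).**

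| Group | Criteria | Stated consequence | Holds a same-dose Period 4? |
|---|---|---|---|
| Within one dose level | 4 | Escalation halted | No |
| Cumulative | 3 | Escalation halted temporarily | No |
| Study stopping | 2 | Study ends | Yes |

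Escalation only: 4 + 3 = 7. Total: 7 + 2 = 9.

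**Step 2. Count the increases (Protocol 7.3, 7.4, 9.3).**

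- Period 1 to 2: 500/200 = 2.5, an increase.
- Period 2 to 3: 1000/500 = 2, an increase.
- Period 3 to 4: 1000/1000 = 1, or less if the dose is lowered. Not an increase.

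Increases left after Period 3: 0. Administrations left: 1, in 16 subjects.

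**Step 3. Put the same event at two levels.** Assume no earlier related SAE.

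| Event | Seen at 500 mg (Period 2) | Seen at 1000 mg fasting (Period 3) |
|---|---|---|
| One related SAE | Halt before 1000 mg | Criterion met, no forced hold before 1000 mg fed; the study rule needs two subjects |
| Severe, non-serious related AEs in two subjects | Halt before 1000 mg | Criterion met, no forced hold; no study rule counts such events |
| Related SAEs in two subjects | Study ends | Study ends |

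The first two rows are the gap. The third shows where the plan already covers Period 4.

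**Step 4. Illustration only.** The documents give no event rates for this setting, so the rates p below are assumptions. Take n = 24 subjects dosed in Period 3, independent, with a common rate.

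Exactly one related SAE meets the escalation criterion but not the study rule: P(X = 1) = 24p(1 − p)^23. For two or more: P(X ≥ 2) = 1 − (1 − p)^24 − 24p(1 − p)^23.

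| Assumed related SAE rate | P(exactly 1) | P(2 or more) |
|---|---|---|
| 0.5% | 10.7% | 0.6% |
| 1% | 19.0% | 2.4% |
| 2% | 30.2% | 8.3% |

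For related severe AEs, the same P(X ≥ 2) gives 8.3%, 33.9% and 70.8% at assumed rates of 2%, 5% and 10%.

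At the SAE rates shown, the single-SAE case, which no fixed rule covers before Period 4, is more likely than the two-SAE case that the study rule covers. The finding rests on Steps 1 to 3, not on these rates.

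**The case against.** The best defence is that Period 4 is already guarded, and most of that is true.

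- **Review is mandatory.** Under 7.5 both bodies assess the data after each level before the next dose, and may lower it or go no further. The synopsis sets out the same review directly after the Period 4 text. The Period 4 dose is to be derived from Part 1 safety and PK data, and 9.5 allows a reduction for safety.
- **One study rule has no numeric threshold.** The SRC, evidently the safety review committee whose minutes 7.5 describes, can end all dosing on the AE pattern, whatever the event type.
- **Tying rules to escalation is coherent.** Period 4 raises no dose. Its subjects have completed Part 1 and are not over 65 (8.1). They have had a washout of at least 14 days (9.2) and a hematology review, and can be withdrawn individually for safety (9.11). Section 4.3.2 reports that a high-fat meal lowered resveratrol absorption, although the food effect for JOTROL is what the study sets out to learn.
- **Any fix still ends in judgement**, and signed minutes with a rationale are already required.

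A reader might infer from the wording of 7.5 that nothing can stop Period 4, or that it could start unreviewed. These safeguards rule out both readings.

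The narrower point survives. Apart from the two study stopping rules, each safeguard is discretionary or applies to one subject at a time; none turns a met escalation criterion into a hold. The same review also precedes Periods 2 and 3, where the sponsor nevertheless added fixed criteria and an agreement rule. The gain from extending them is a changed default and a formal agreement requirement: modest, but real.

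**Conclusion.** The point holds as a gap in the scope of the rules. Seven of nine criteria, and the agreement rule, have no automatic effect on the planned repeat of the top dose in 16 subjects. The clearest case is a single related SAE in Period 3.

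This assumes the nominal scheme. The synopsis allows intermediate levels, and doses are reassessed after each period, so Period 3 may not be at 1000 mg and a further step could be added. The gap would then follow the last Part 1 level.

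A reader might also take the probabilities above as evidence that a criterion is likely to be met. The documents do not support that. The 12-week Friedreich's ataxia study in 4.3.1 reported no SAEs among 27 treated participants and describes 1,000 mg/day as well tolerated, and 7.1 does not call the gastrointestinal symptoms severe. The sponsor should consider the change because it closes the gap with little text, not because an event is expected.

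**What to change.** Add to Protocol 7.5, with a reference from 7.4 and 9.5, text to this effect:

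> If any criterion for halting escalation is met at a dose level, that level will not be repeated, and Period 4 will not be given at that level, unless the Safety Committee and the DSMB mutually agree and record the reason in the signed minutes. Otherwise Period 4 will use a lower Part 1 dose level at which no criterion was met, or will not be run.

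Keep the existing halt on higher doses, the AUC limit and the two study stopping rules. Restricting the fallback to a level already given fasting preserves the same-dose fed/fasting comparison in Protocol 12.3 and SAP 10.5.4.

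**Cost.** The amendment is a few sentences. No extra meeting is needed, since both bodies already review the data before the next dose. The real price falls on the food-effect objective: after a criterion is met, Period 4 may be delayed, dropped, or run at 500 or 200 mg under the nominal scheme. At a lower dose AUC0-inf may be harder to obtain. In Protocol Table 1 it could be established in only one participant at 0.5 g of resveratrol, although JOTROL may do better.
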